4.1.2. Safety Set (SS)

Safety Set will include all subjects who have been treated with the device at least once and have safety evaluation data. SS will be the main data set for other safety analysis excepting the primary safety endpoints.

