8.9 Subject selection criteria and reasons

- (1) Full analysis set (FAS): According to the basic principles of Intention to Treat (ITT), FAS refers to the set of subjects that comply with the ITT principles. It includes:
- a) Subjects who have been treated with the investigational device, achieved the immediate operation success, and have at least one observation data of primary endpoints after baseline;
 - b) Subjects who have received treatment with the investigational device, but have failed in the implantation because of the device itself, regardless of whether there is test device in the body.

If the implantation is abandoned due to other clinical reasons and there is no investigational device in the body, such subjects will not be included in the FAS. The definition of receiving the investigational device treatment is that if any part of the device, including the occluder itself and its delivery device, contact with human body through vascular approach, it can be considered as receiving the device treatment. FAS will be the main data set for baseline data analysis, primary safety and efficacy evaluation.

- (2) Per protocol set (PPS): refers to subjects who have no serious violation of the study protocol in FAS, have good compliance, have not used drugs or treatments that may affect the efficacy evaluation during the trial, and have no missing data of primary endpoints. Unless otherwise specified, no carrying forward will be performed for the missing data of PPS. Theoretically, PPS should exclude subjects who have not completed all the visit plans due to various reasons, except that whether the subject's ASD has been successfully treated can be judged according to the existing results. PPS will be the secondary data set for efficacy evaluation.
- (3) Safety set (SS): It is used for safety evaluation of the clinical trial, including all subjects who have been treated with the device at least once. SS will be the main data set of safety analysis.
- (4) The efficacy evaluation of the device is mainly based on FAS, and PPS is only used as a reference data set for efficacy evaluation. Safety evaluation is based on SS. According to the above criteria, the subjects will be included in FAS, PPS and SS for interim efficacy evaluation and analysis at 360-day post operation. In the fifth year after operation, the subjects will be also included in FAS, PPS and SS for finally efficacy evaluation

and analysis according to the above criteria.

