3.2.2. Secondary Endpoints

Immediate operation success rate, which means that left and right disks are effectively fixed on the left and right sides of the atrial septum, respectively, and smoothly released without displacement or migration, and the delivery system is successfully withdrawn.

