4.1.1. Full Analysis Set (FAS)

Full analysis set (FAS): According to the basic principles of Intention to Treat (ITT), FAS refers to the set of subjects that comply with the ITT principles. It includes:

- a) Subjects who have been treated with the investigational device, achieved the immediate operation success, and have at least one observation data of primary endpoints after baseline;

- b) Subjects who have received treatment with the investigational device, but have failed in the implantation because of the device itself, regardless of whether there is a study device in the body.

If the implantation is abandoned due to other clinical reasons and there is no investigational device in the body, such subject will not be included in the FAS. The definition of receiving the investigational device treatment is that if any part of the device, including the occluder itself and its delivery device, contact with human body through vascular approach, it can be considered as receiving the device treatment. FAS will be the main data set for baseline data analysis, primary safety, and efficacy evaluation.

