5. ENDPOINTS ANALYSIS

5.1. Primary Endpoints Analysis

For primary efficacy endpoints and safety endpoints, statistical inference will be based on the FAS and PPS. The FAS will serve as the primary dataset for primary endpoint analyses, while the PPS will be the secondary dataset.

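### A listed complication that itself stops the implantation can drop out of the co-primary safety test, because the FAS omits or leaves unassigned non-device implantation failures

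*SAP*

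**What the plan says.** **Which set.** Protocol 8.9 item (1) states: "FAS will be the main data set for baseline data analysis, primary safety and efficacy evaluation". Item (3) then states "SS will be the main data set of safety analysis" and item (4) "Safety evaluation is based on SS", neither with an exception for the primary endpoint. The SAP chooses the FAS: section 4.1.2 has "SS will be the main data set for other safety analysis excepting the primary safety endpoints", and section 5.1 has "The FAS will serve as the primary dataset for primary endpoint analyses, while the PPS will be the secondary dataset".

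**Who is in the FAS.** Protocol 8.9 and SAP 4.1.1 use essentially the same definition. A subject counts as treated once any part of the occluder or delivery device has entered through a vessel. A treated subject joins the FAS by one of two limbs:
- (a) immediate operation success plus at least one primary-endpoint observation after baseline;
- (b) implantation failure caused by the device itself.

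The stated exclusion is: "If the implantation is abandoned due to other clinical reasons and there is no investigational device in the body". Immediate success requires that the discs are "smoothly released without displacement or migration, and the delivery system is successfully withdrawn" (SAP 3.2.2).

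**Who is in the SS.** SAP 4.1.2: "all subjects who have been treated with the device at least once and have safety evaluation data".

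**Which events.** Protocol 7.1.7.1 lists seven common complications, including occluder displacement, high-grade AV block and air embolism. Protocol 13.1.4.1 item (2) describes third-degree AV block during the operation that does not recover as leading to abandonment of the procedure.

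**Relatedness.** Protocol 7.1.7.2 counts adverse events judged unlikely to be related as device-related. SAP 6.1.1 puts them with the unrelated events.

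**The concern.** In a single-arm trial the safety set should not depend on the safety outcome. Here it can. If a complication on the list causes the implantation to be given up, and the cause is judged not to be the device, the subject can leave the set in which that complication would have been counted. The PPS cannot recover the subject, because it is drawn from the FAS. No planned table tests the 6% criterion in everyone who had device contact.

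Both primary endpoints must succeed, and the exact rule tolerates only two or three events, so where one subject is placed can settle the trial. That placement depends on a judgement of cause, made in an open study, for which the documents give no adjudication rule.

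**Working it through.** **1. The plan's own figure.** Inputs from Protocol 8.2.1: OPC 6%, target 1%, one-sided alpha 0.025, power 80%, normal approximation.

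n = [1.960·√(0.06·0.94) + 0.842·√(0.01·0.99)]² / 0.05² = 120.65, so 121, with power 0.802. This agrees with the protocol. Its 146 is 121 × 1.2 = 145.2, rounded up. The SAP plans 142 (section 3.1), so both sizes are used below.

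**2. The decision rule.** SAP 5.1.2 requires the upper limit of the exact two-sided 95% interval to be below 6%. With x events in n subjects, that limit is the 0.975 quantile of Beta(x+1, n−x). The largest passing count is 2 for n = 118 to 143 and 3 for n = 144 to 167.

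**3. How a listed event can leave the FAS.**
- *Displacement at release.* This is not immediate success, so limb (a) fails. Protocol 7.1.7.1 attributes displacement to anatomy, sizing or operation. On that attribution limb (b) fails too, and with the device still in the body no rule assigns the subject. If the cause is judged to be the device, limb (b) keeps the subject. Displacement after a successful release stays in through limb (a).
- *Unrecovered intraoperative AV block.* The procedure is abandoned. If the reason is classed as non-device and no device remains, the exclusion applies. This matters only if intraoperative events count towards the endpoint, which is not explicit. The endpoint is worded as post-operative, and Protocol 7.2.2 collects complications at Visits 1 to 5. Yet air embolism is defined as arising from the implantation itself, and SAP 6.1 includes intraoperative events in its adverse-event tables.

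**4. What one placement does.**

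| Omitted from the FAS | All treated | FAS |
|---|---|---|
| 1 subject with an event | 3/142: 6.05%, fail | 2/141: 5.03%, pass |
| 1 subject with an event | 4/146: 6.87%, fail | 3/145: 5.93%, pass |
| 3 event-free subjects | 3/146: 5.89%, pass | 3/143: 6.01%, fail |

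Starting from 142, event-free omissions cannot turn a pass into a fail until n falls below 118.

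**5. Both effects together.** Let e be the share of treated subjects with an event that prevents FAS entry, and f the share abandoned and event-free. The documents give neither, so both are assumptions. The total rate r is 1% and no data are missing. The FAS rate is o = (r−e)/(1−e−f), and k(n) is the largest passing count.
- All treated: P(Bin(N, r) ≤ k(N)).
- FAS: the sum over j of P(Bin(N, e+f) = j) × P(Bin(N−j, o) ≤ k(N−j)).

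| N | e, f | Pass, all treated | Pass, FAS |
|---|---|---|---|
| 146 | 0.1%, 1% | 94.0% | 93.5% |
| 146 | 0.1%, 2% | 94.0% | 89.7% |
| 146 | 0.25%, 1% | 94.0% | 95.5% |
| 146 | 0.25%, 2% | 94.0% | 92.9% |
| 142 | 0.1%, 1% or 2% | 82.9% | 86.3% |
| 142 | 0.25%, 1% or 2% | 82.9% | 90.8% |

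With a true rate of 6% in all treated subjects, the false-pass probability at N=146 is 2.21% for all treated. In the FAS it is 2.06% (0.1%, 1%), 1.38% (0.1%, 2%), 2.30% (0.25%, 1%) or 2.88% (0.25%, none). At N=142 it is 0.78% against 0.88% or 1.05%.

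**6. Imputation matters more than the set.** SAP 4.2 imputes incomplete safety follow-up as a complication (NRI). If 1% of treated subjects, abandoned and event-free, entered the set and were all scored as events, the pass probability would fall from 94.0% to 66.5% (N=146) or from 82.9% to 45.8% (N=142).

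**The case against.** The strongest reply is that the set is already settled. Protocol 8.9 uses the words primary safety only for the FAS, a specific sentence governs general ones, and the SAP confirms the choice openly. That stands: items (3) and (4) need tidying and do not create a live conflict. A reader might also infer that the SAP drifted from the protocol. It did not, because SAP 4.1.1 repeats the protocol's FAS wording.

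The routes are indeed narrow, as step 3 shows, and the shares in step 5 are assumed. Sensitivity to one event is common to any exact test with so small a limit. The documents also disclose such cases elsewhere: omitted events would appear in the descriptive adverse-event tables on the SS, and failed implantations bear on the immediate success rate. All of this limits the weight of the point. It does not remove it, because none of those tables decides the 6% criterion, and the exclusion applies even when a listed complication caused the abandonment.

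Finally, bringing subjects without a device into the test raises the question of whether NRI or the 5 mm residual-shunt item applies to them. Waiving either would depart from SAP 4.2 in the device's favour, so it belongs only in a labelled sensitivity analysis.

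**Conclusion.** The point holds as a gap in the rules: the FAS definition lets a listed complication that stops the implantation fall outside the co-primary safety test, or leaves its place undecided. One such event can reverse the result at either planned size.

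Two stronger readings are tempting and are not supported. The first is that the FAS favours the device. Omitting an event does, but omitting event-free subjects can work the other way at N=146, and the sign changes across the assumed shares. The second is that error control is lost. Only one scenario computed exceeds 2.5% (2.88%, with no event-free abandonment at all), and at N=142 the highest is 1.05%. These figures rest on assumed shares and on intraoperative events counting. The case for acting is that the rule should be fixed before the data show which way it falls.

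The relatedness mismatch is a direct contradiction but minor. It concerns a descriptive endpoint, and the SAP grouping can only give a rate equal to or below the protocol's. It adds no weight to the main point.

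**What to change.** 1. **SAP 4.1.1:** assign every treated subject with a failed or abandoned implantation, including non-device failure with a device in the body. Keep in the primary safety analysis any treated subject in whom a listed complication occurred. Alone, this retains subjects with events while event-free ones may stay out, so it needs item 3 beside it.
2. **SAP 5.1.2:** state that listed complications occurring during the procedure count.
3. **SAP 5.1.2:** report the 6% test also in all subjects with device contact, on observed complications, alongside the FAS. Define this set by device contact, since the SAP's SS also requires safety evaluation data. Show event-free subjects left without a device with and without NRI, as a labelled sensitivity analysis.
4. **Protocol 8.9:** align items (3) and (4) with item (1) and the SAP.
5. **Minor:** reconcile Protocol 7.1.7.2 with SAP 6.1.1, map the result to the Protocol 13.1.3 categories (the nearest to the disputed label is Possibly irrelevant), and show both groupings.

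The cost is wording in two documents and one or two extra tables. The reported complication and device-related event rates may look slightly less favourable.

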4.1.3. Per-Protocol Set (PPS)

Per-Protocol Set refers to subjects who have no serious protocol deviation in FAS, have good compliance, have not used drugs or treatments that may affect the efficacy evaluation during the trial, and have no missing data of primary endpoints. Unless otherwise specified, no carrying forward will be performed for the missing data of PPS. Subjects who did not complete the full visit schedule for any reason should theoretically be excluded from the PPS. However, this exclusion does not apply if existing results already determine whether the subject successfully underwent treatment for atrial septal defect. treated can be judged according to the existing results. PPS will be the secondary data set for efficacy evaluation.

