7.1.5.3 Dropout Criteria and management

Subjects who have signed informed consent forms and are screened qualified quit the trial and fail to complete the observation period specified in the protocol are called dropout cases, regardless of when and why. The criteria for dropout are as follows:

- (1) For whatever reason, the subject is unwilling or impossible to continue the clinical trial, and requires to withdraw from the clinical trial.
- (2) Although the subject does not explicitly propose to withdraw from clinical trial, he/she no longer receive treatment and examination and loses to follow-up
- (3) The subject presents SAE, and the investigator judges that the subject should withdraw from the clinical trial.
- (4) The subject has poor compliance.

Dropout management: For all dropout cases, the summary form of clinical trial completion should be filled in the original records and the reasons for dropout should be analyzed. When the subject drops out, the investigator should contact the subject as much as possible, inquire the reason and record the last clinical symptom, and complete the evaluation items that can be achieved. If the subject withdraws from the trial due to AE, the investigator should take corresponding treatment actions according to the actual situation of the subject.

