13.1.4 Possible AEs in this trial and corresponding treatments

13.1.4.1 Common complications and corresponding treatments

- (1) Occluder dislocation: Preoperative multi-sectional measurements of ASD size are helpful for selection of indications and occluders. Improper selection of occluder can easily cause dislocation. Through observing the position of the development site and the shape of the left and right discs of the occluder by TTE combined with chest X-ray, it can be judged whether the occluder falls off. If the occluder falls off, it should

be taken out with catcher. If the occluder is large or difficult to take out, the emergency surgery should be performed.

- (2) High-grade atrioventricular block: If degree III atrioventricular block occurs during the operation and is still not recovered after long-term suspension of operation, the interventional therapy should be abandoned; Drug treatment should be given in time if degree III atrioventricular block occurs after operation. The device should be removed by surgery and ASD should be repaired if the drug therapy is ineffective;
- (3) Cardiac tamponade: Cardiac tamponade can be judged by TTE. Emergent pericardial puncture should be performed for blood drainage and decompression to relieve tamponade, temporarily change the hemodynamics, and contend for rescue time. Meanwhile, saline and blood should be infused to correct hemorrhagic shock. Furthermore, emergency thoracotomy exploration should be prepared. Strict anesthesia management is required and cardiac arrest should be strictly prevented. Sufficient blood should be replenished. Blood accumulated in pericardium cavity should be removed during operation. Normal systolic and diastolic function of heart should be restored. Heart damage should be repaired accurately. Close monitoring of cardiac function and rational application of cardiovascular active drugs are required after operation;
- (4) Air embolism: It can be judged by TTE combined with chest X-ray. Oxygen should be inhaled immediately, atropine should be given to patients with slow heart rate, and nitroglycerin should be adopted at the same time to prevent vasospasm;
- (5) Residual shunt above medium: It can be judged by TTE. If the diameter of residual shunt is larger than 5 mm and has hemodynamic significance, it is recommended to block the residual shunt again;

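### The SAP tests the primary safety endpoint in the per-protocol set, whose efficacy-based membership rules can exclude a subject because of the complication being counted, so this secondary rate can be biased downward.

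*SAP*

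**What the plan says.** **Who is in the PPS.** SAP 4.1.3 starts from FAS subjects without serious deviations and with good compliance, and requires that they "have not used drugs or treatments that may affect the efficacy evaluation during the trial, and have no missing data of primary endpoints". It adds: "Subjects who did not complete the full visit schedule for any reason should theoretically be excluded from the PPS". One exception follows: "this exclusion does not apply if existing results already determine whether the subject successfully underwent treatment for atrial septal defect". The section ends by calling the PPS the secondary set for efficacy.

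**What the PPS is used for.** SAP 5.1 states: "For primary efficacy endpoints and safety endpoints, statistical inference will be based on the FAS and PPS". The FAS is primary and the PPS secondary. SAP 5.1.2 confirms a PPS analysis of the complication rate, without imputation. Protocol 8.9(4) gives the PPS a narrower role: "PPS is only used as a reference data set for efficacy evaluation. Safety evaluation is based on SS".

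**What can follow a counted complication.** Protocol 13.1.4.1 describes retrieval or surgery for a dislodged occluder. For third-degree AV block after the operation it says: "The device should be removed by surgery and ASD should be repaired if the drug therapy is ineffective". For a residual shunt larger than 5 mm with haemodynamic significance, "it is recommended to block the residual shunt again". Protocol 7.1.5.3(3) lists this as a dropout criterion: "The subject presents SAE, and the investigator judges that the subject should withdraw from the clinical trial".

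**Safety decision rule.** Under SAP 5.1.2 the endpoint is met if the upper limit of the exact two-sided 95% interval for the complication rate is below 6%.

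**The concern.** The safety endpoint is the occurrence of any of seven listed complications during 360 days. Once one has been observed, the subject's outcome is settled, whatever is done or missed afterwards.

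The PPS rules look at what happens after implantation and are written with closure in mind. Applied to the safety endpoint, they can make membership depend on the consequences of the event itself. Someone whose shunt was closed again, or whose device was removed, may be judged to have had a treatment affecting the efficacy evaluation. Someone withdrawn after a serious event may lack the day-360 closure value and the later visits. In both cases a known event leaves the numerator and the denominator.

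The PPS complication rate could then appear to support the FAS result, or to contradict it, for a reason unrelated to protocol adherence. This matters because the SAP calls the PPS result statistical inference on a co-primary endpoint, and SAP 3.1 says the 360-day analysis supports the marketing application.

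**Working it through.** **1. The plan's own figures.** Protocol 8.2.1 uses a 6% criterion, a 1% target, one-sided alpha 0.025 and 80% power:

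n = [(1.960·√(0.06·0.94) + 0.842·√(0.01·0.99)) / 0.05]² = 120.65, so 121, as stated.

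The total of 146 follows from 121 × 1.2 = 145.2. The SAP plans 142 subjects (3.1), so both totals are used below.

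**2. Events the safety rule allows.** The exact (Clopper-Pearson) upper limit for x events in n subjects is the 0.975 quantile of a Beta(x + 1, n − x) distribution.

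| n | x | Upper limit | Below 6%? |
|---|---|---|---|
| 142 | 2 | 5.00% | yes |
| 142 | 3 | 6.05% | no |
| 146 | 3 | 5.89% | yes |
| 146 | 4 | 6.87% | no |

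**3. Removing subjects who had an event.** Each removal lowers x and n by one.

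| All events counted | Removed | After removal | Result |
|---|---|---|---|
| 3/142, 6.05% | 1 | 2/141, 5.03% | fail becomes pass |
| 4/142, 7.06% | 1 | 3/141, 6.09% | still fails |
| 4/142, 7.06% | 2 | 2/140, 5.07% | fail becomes pass |
| 4/146, 6.87% | 1 | 3/145, 5.93% | fail becomes pass |
| 5/146, 7.81% | 1 | 4/145, 6.91% | still fails |
| 5/146, 7.81% | 2 | 3/144, 5.97% | fail becomes pass |

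**4. Event-free subjects leaving as well.** Starting from 3/142, remove one subject with an event and 24 without: 142 − 25 = 117, and 2/117 has an upper limit of 6.04%, a fail. Starting from 4/146, remove one with an event and two without: 146 − 3 = 143, and 3/143 gives 6.01%, also a fail. Ordinary attrition can therefore cancel the flip.

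**5. Operating characteristic.** Let the true complication rate be 6%, and let each subject with a complication leave the PPS independently with probability f, with no event-free subject leaving. The documents give no value for f, so a range is shown. The chance that the PPS test passes is:

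| f | n = 142 | n = 146 |
|---|---|---|
| 0 | 0.8% | 2.2% |
| 0.25 | 4.3% | 7.7% |
| 0.50 | 20% | 21% |
| 0.75 | 64% | 63% |

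Because event-free attrition is set to zero, these values show how sensitive the test is. They are not a forecast.

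**6. Does the exception in SAP 4.1.3 prevent this?** It relaxes only the incomplete-visit rule, and it turns on whether the outcome of the ASD treatment is known. It does not lift the treatment criterion. It also has no counterpart for a subject whose complication is known but whose closure outcome is not, for example one withdrawn after a cerebral embolism.

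**The case against.** The strongest reply is that the SAP nowhere says that treating a complication excludes a subject. The treatment criterion may be aimed at confounding concomitant treatment, and incomplete subjects are excluded only in theory. This stands. Exclusion is possible under the text but not prescribed by it, so a reader who infers that the PPS removes every re-operated or withdrawn subject goes further than the documents do.

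The exception also has real reach. A residual shunt of 5 mm or more is the complement of effective closure, and a displaced or removed occluder is arguably a settled closure failure, so such subjects may survive the incomplete-visit rule. The treatment criterion remains open for them.

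The routes out of the PPS are conditional. Removal for AV block depends on failed drug therapy, repeat closure on haemodynamic significance, and withdrawal after a serious event on the investigator's judgement. Protocol 7.1.5.3 also asks for whatever evaluations can still be done at dropout. Complications with neither re-intervention nor withdrawal stay in.

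Finally, the FAS is the primary set, and SAP 4.2 and 5.1.2 impute incomplete safety follow-up there as a complication. This limits the point to a secondary analysis. It does not explain why the SAP takes safety inference to a set that its own section 4.1.3 describes as serving efficacy.

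**Conclusion.** The point holds for the secondary PPS analysis of the primary safety endpoint. The SAP disagrees with itself and with protocol 8.9 on whether the PPS serves safety, and the membership rules leave room to exclude a subject because of an observed complication, its re-intervention or a resulting withdrawal. Any such exclusion lowers the PPS complication rate. With 2 or 3 events allowed, a single one can reverse the PPS result, though attrition among event-free subjects can cancel this. The size rests on an assumed number of exclusions that the documents do not give.

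Two stronger readings are not supported. One is that the trial's main safety conclusion is at risk: that conclusion rests on the FAS with conservative imputation, which these rules do not touch. The other is that the PPS closure rate is necessarily biased upward: the documents do not say how a re-closed subject is scored at day 360, so that direction is not established.

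The text should be corrected before database lock, but the primary analysis needs no change.

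**What to change.** **Preferred.** Delete the PPS from inference on the primary safety endpoint in SAP 5.1 and 5.1.2. This agrees with SAP 4.1.3 and with the efficacy-only role in protocol 8.9.

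**If the PPS safety analysis is kept.** Add to SAP 4.1.3 and 5.1.2: *For the PPS analysis of the primary safety endpoint, any FAS subject with an observed common complication is retained and counted as an event, regardless of later treatment or missed visits. This retention applies to the safety analysis only and does not alter membership or closure scoring in the PPS efficacy analysis.* The second sentence is needed so that re-closed subjects do not enter the PPS efficacy analysis without a rule for scoring them.

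**Cost.** A short SAP edit before database lock, with no new data and no change to the FAS analysis. Under the second option the PPS complication rate may look slightly less favourable.
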